3.7. Data Handling Conventions and Transformations

In general, age collected at Day 1 (in years) will be used for analyses and presented in listings. If age at Day 1 is not available for a participant, then age derived based on date of birth and the first dose date will be used instead. If an enrolled participant was not dosed with any study drug, the enrollment date will be used instead of the Day 1 visit date. For screen failures, the date the first informed consent was signed will be used for the age derivation.

Laboratory data that are continuous in nature but are less than the lower limit of quantitation (LOQ) or above the upper LOQ will be imputed as follows:

- A value that is 1 unit less than the LOQ will be used to calculate descriptive statistics if the datum is reported in the form of "< x" (where x is considered the LOQ). For example, if the values are reported as < 50 and < 5.0, values of 49 and 4.9, respectively, will be used to calculate summary statistics. An exception to this rule is any value reported as < 1 or < 0.1, etc. For values reported as < 1 or < 0.1, a value of 0.9 or 0.09, respectively, will be used to calculate summary statistics.
- A value that is 1 unit above the LOQ will be used to calculate descriptive statistics if the datum is reported in the form of "> x" (where x is considered the LOQ). Values with decimal points will follow the same logic as above.
- The LOQ will be used to calculate descriptive statistics if the datum is reported in the form of " \leq x" or " \geq x" (where x is considered the LOQ).

3.8. Analysis Visit Windows

3.8.1. Definition of Study Day

Study Day 1 is defined as the first dosing date of study drug.

Study Days are calculated relative to Study Day 1 and derived as follows:

- For postdose study days: Assessment Date First Dosing Date + 1
- For days prior to the first dose: Assessment Date First Dosing Date

Therefore, **Study Day 1**/ **First Dose Date** is the day of first dose of study drug administration, as recorded on the Study Drug Administration eCRF form.

Last Dose Date is defined as the maximum, nonmissing, nonzero dose end date of treatment recorded on the Study Drug Administration eCRF form with "Study Drug Permanently Withdrawn" box checked for participants who prematurely discontinued or completed study drug according to the Study Drug Completion eCRF. Refer to Appendix 2 for missing date imputation, if necessary.

Last Study Date is the latest of the study drug start dates and end dates, the clinic visit dates, the laboratory visit dates including the 28-day follow-up visit date, and the death date (if applicable, only for participants who prematurely discontinued study according to the Study Completion eCRF).

Baseline value is defined as the last value obtained on or prior to the first dose date (and time, if available) unless otherwise specified (see Section 3.8.3).

3.8.2. Analysis Visit Windows

Participant visits might not occur on protocol-specified days. Therefore, for the purposes of analysis, observations will be assigned to analysis windows. The study day as defined in Section 3.8.1 will be used when data are summarized by visit.

Vital signs were to be collected daily; therefore, windows are not assigned and results will be summarized for each Study Day, except for Study Day 28. For Study Day 28, the nominal day is Study Day 28, the lower limit is Study Day 15 and there is no upper limit.

Ordinal scale results were to be recorded prior to dosing on Study Day 1. The worst result for each day from Day 1 (after first dose) through the earliest of discharge date or Day 14 was to be recorded. For participants who were discharged after Day 14, changes in score category were to be recorded each day from Day 15 to the earliest of discharge date or Day 28. For the ordinal scale, baseline is defined as the value recorded prior to dosing, or the last value obtained prior to the first dose date if the predose value was not recorded on the day of dosing. Results will be summarized for each Study Day without windows. If more than one result was reported on the same day, the worst result will be selected.

The analysis windows for hematology and chemistry laboratory parameters are presented in Table 3-1.

Table 3-1. Analysis Windows for Hematology and Chemistry Laboratory Tests (hemoglobin, hematocrit, platelet count, WBC, ALT, AST, total bilirubin, glucose, serum creatinine, and creatinine clearance)

Visit ID	Nominal Day	Lower Limit	Upper Limit	
Baseline/Day 1	1		1 (predose)*	
Day 3	3	1 (postdose)*	3	
Day 5	5	4	6	
Day 8	8	7	8	
Day 10	10	9	11	
Day 14	14	12	15	
Post Day 14**	28	16		

^{*} For Baseline, the upper limit includes values collected at or prior to the first dose date/time. For Day 3, the lower limit includes values collected after the first dose date/time on Day 1.

3.8.3. Selection of Data in the Event of Multiple Records for an Analysis Visit Day

Depending on the statistical analysis method, single values may be required for each Study Day/ analysis window. For example, change from baseline by visit usually requires a single value, whereas a time-to-event analysis does not require 1 value per Study Day or analysis window.

If multiple valid, nonmissing measurements exist for a Study Day/analysis window, records will be chosen based on the following rules if a single value is needed:

- For baseline, the last nonmissing value on or prior to the first dosing date (and time, if available) of study drug will be selected, unless specified differently. If there are multiple records with the same time or no time recorded on the same day, the baseline value will be the average of the measurements for continuous data, or the measurement with the lowest severity for categorical data.
- For postbaseline values:

For windows spanning multiple days, the record(s) collected on the day closest to the nominal day will be selected. If there are 2 days equidistant from the nominal day, the later day will be selected.

- For laboratory values and SpO2 and partial pressure of oxygen, arterial (PaO2), if there is more than 1 record on the selected day, the worst value will be selected. See Appendix 2 for definition of worst value.
- For other parameters, if there is more than 1 record on the selected day, the average will be taken for continuous data and the worst severity will be taken for categorical data, unless otherwise specified.

^{**} Post Day 14 laboratory values will be considered for treatment emergent laboratory presentations only.

4. SUBJECT DISPOSITION

4.1. Subject Enrollment and Disposition

The number and percentage of participants enrolled at each investigator site will be summarized using the Expanded RDV-Treated Analysis Set. The denominator for this calculation will be the number of participants in the Expanded RDV-Treated Analysis Set.

The summary of subject disposition will be provided for all screened participants. This summary will include the number of participants screened, screen failure participants who were not enrolled, participants who met all eligibility criteria and were not enrolled, participants enrolled, participants enrolled but never treated, and participants in the Expanded RDV-Treated Analysis Set.

In addition, the number and percentage of the participants in the following categories will be summarized:

- Completed 10-day treatment on study drug as recorded on the Study Drug Completion form
- Prematurely discontinuing study drug prior to completion of 10 days of dosing with summary of reasons for discontinuing study drug as recorded on the Study Drug Completion form
- Completed study
- Prematurely discontinuing from study with summary of reasons for discontinuing study as recorded on the Study Completion form.

The denominator for the percentages of participants in each category will be the number of participants in the Expanded RDV-Treated Analysis Set.

A data listing of reasons for study drug/study discontinuation will be provided.

4.2. Extent of Study Drug Exposure

4.2.1. Exposure to Study Drug

Number of doses received will be summarized for participants in the Expanded RDV-Treated Analysis Set.

4.3. Protocol Deviations

A listing will be provided for all enrolled participants who violated at least 1 inclusion or exclusion criterion. The listing will include the criteria not met.

Protocol deviations occurring after participants entered the study are documented during routine monitoring. The number and percentage of participants with important protocol deviations by deviation reason and the total number of important protocol deviations by deviation reason (eg, nonadherence to study drug, violation of select inclusion/exclusion criteria) will be summarized for the Expanded RDV-Treated Analysis Set. A by-subject listing will be provided for those participants with important protocol deviations.

5. BASELINE CHARACTERISTICS

5.1. Demographics and Baseline Characteristics

Participant demographic data (eg, sex, race/ethnicity, and age) and baseline characteristics (eg, body weight, height, and body mass index [BMI]) will be summarized using descriptive statistics (n, mean, SD, median, Q1, Q3, minimum, and maximum) for continuous data and by the number and percentage of participants for categorical data. The summaries of demographic data and baseline participant characteristics will be provided for the Expanded RDV-Treated Analysis Set.

Age group (< 65 and ≥ 65) will be summarized.

A by-subject demographic listing will be provided.

5.2. Other Baseline Characteristics

The following baseline disease characteristics will be summarized using descriptive statistics:

- Clinical status (7-point ordinal scale)
- Duration of hospitalization prior to first dose of RDV
- Duration of symptoms prior to first dose of RDV
- AST
- ALT
- Oxygen support status based on the 7-point ordinal scale (low-flow oxygen, room air)
- Region (North America, Europe, Asia)

5.3. Medical History

Any medical condition or clinically significant laboratory abnormality with an onset date before the consent form is signed and not related to a protocol-associated procedure is considered to be preexisting and should be documented as medical history. General medical history data will be collected at screening and coded using MedDRA. A summary table will present the percentages of participants reporting each medical history preferred term, sorted first in alphabetical order by system organ class and then by preferred term (PT) in descending order of total frequency within system organ class. Preferred terms with the same total frequency will be sorted in alphabetical order.

6. EFFICACY ANALYSES

6.1. Primary Efficacy Endpoint

The primary efficacy endpoint was analyzed for Part A of the study and is not described in this SAP.

6.2. Efficacy Endpoints of Interest

Efficacy endpoints of interest include endpoints based on clinical status assessed by a 7-point ordinal scale. The endpoint will be derived by combining the available death, hospital discharge alive and ordinal scale assessment reported by the site, where death supersedes discharge alive and discharge alive supersedes the ordinal scale score reported by the site. The proportion of participants for each ordinal scale category is expressed as percentages for presentation purpose.

Sites were instructed to report the worst ordinal scale category for each day. Therefore, the ordinal scale result on the day the participant was discharged alive does not necessarily reflect Not hospitalized (7). The definition of clinical status based on the 7-point ordinal scale is defined as follows:

- If a participant dies while hospitalized (as recorded on the Death eCRF and Hospitalization eCRF), the endpoint on the day of death and all subsequent days through Day 28 will be set to Death (1)
- If the participant is discharged alive, the endpoint on the day of discharge alive and all subsequent days through Day 28 will be set to Not hospitalized (7)
- If the participant is discharged alive and dies on the same day or a later day (as recorded on the Death eCRF and Hospitalization eCRF), the endpoint on the day of discharge alive and all subsequent days until the day of death will be set to Not hospitalized (7). On the day of death and all subsequent days through Day 28, the endpoint will be set to Death (1),

Every effort will be made to obtain clinical status data for all participants prior to discharge alive. The last known clinical status will be used for days with missing clinical status (eg, where the reason for Hospital Discharge is not "Discharged Alive" and the participant has not died). All post-baseline days with missing ordinal scale score, from Day 2 to Day 14 and Day 28, will use the previous last known clinical status.

Efficacy endpoints of interest include

- Clinical status on Days 1 to 14, Day 28 and last available assessment
- Change in clinical status on Days 5, 7, 11, 14, 28, and last available assessment
- Time to clinical improvement (days): Clinical improvement is defined as a ≥ 2-point improvement from baseline clinical status or discharged alive on the 7-point ordinal scale using the definition specified above.

- Percentage of participants with a ≥ 2-point improvement or discharged alive based on the 7-point ordinal scale using the definition specified above on Day 5, Day 7, Day 11, Day 14, Day 28, and last available assessment
- Time to \geq 1-point improvement (days) from baseline clinical status on the 7-point ordinal scale using the definition specified above.
- Percentage of participants with a ≥ 1-point improvement based on the 7-point ordinal scale using the definition specified above on Day 5, Day 7, Day 11, Day 14, Day 28 and last available assessment
- Time to recovery based on the 7-point ordinal scale using the definition above, where recovery is defined as an improvement from a baseline score of 2 through 5 to a score of 6 or 7, or an improvement from a baseline score of 6 to a score of 7
- Percentage of participants with recovery based on the 7-point ordinal scale using the definition specified above on Day 5, Day 7, Day 11, Day 14, Day 28 and last available assessment
- Number of days of oxygen support while hospitalized through discharge alive, death or Day 14 based on the 7-point ordinal scale reported values (See Appendix 2). This summary will present results separately for participants who died on or prior to Day 14 and those who were discharged alive on or prior to Day 14 and will include:

Days on invasive mechanical ventilation

Days on high-flow oxygen devices

Days requiring low-flow supplemental oxygen

Because oxygen support status was collected only while the participant was in the hospital, if a participant was discharged alive and died afterwards, the participant will be included only in the summary for participants discharged alive. Oxygen support status is defined based on the 7-point ordinal scale (See Appendix 2)

- Shift in oxygen support status from baseline to Days 5, 7, 11, 14, 28 and last available assessment
- Duration of hospitalization (days) (duration from hospital admission and duration from Day 1). Duration of hospitalization is calculated through Days 11 and 28 for participants who were discharged alive prior to Days 11 and 28, respectively. If participants were rehospitalized for COVID-19 related reasons, the hospitalization discharge information is entered in the eCRF database using the latest hospitalization admission.
- All-cause mortality

6.2.1. Analysis of Efficacy Endpoints of Interest

The number and percentage of participants in each clinical status category for each day from Baseline through Day 14 and at Day 28 and using the last available assessment will be summarized. These results will be summarized using (1) the clinical status definition in Section 6.2 and (2) with the definition specified in Section 6.2 but excluding days with missing ordinal scale score not due to death or discharge alive. In addition, stacked bar charts by study day (Baseline through Day 14 and at Day 28) will be produced using the definition specified in Section 6.2.

The number and percentage of participants in each clinical status category for each day from Baseline through Day 14 and at Day 28 and last available assessment will be summarized within each subgroup defined in Section 3.4.1.

The change from baseline in clinical status category on Days 5, 7, 11, 14, 28 and last available assessment will be summarized by group using descriptive statistics.

Number of days of oxygen support status modes (invasive mechanical ventilation, high flow oxygen, low flow oxygen) will be calculated as the number of days oxygen support was reported on the 7-point ordinal scale eCRF through death, discharge alive, or Day 14 and presented using descriptive statistics.

A shift table of baseline oxygen support status (death, invasive mechanical ventilation, high flow oxygen, low flow oxygen, room air, discharge alive) to Days 5, 7, 11, 14, 28 and the last available status will be included.

Duration of hospitalization will be calculated only for participants who are discharged alive on or prior to Days 11 and 28 and will be summarized using descriptive statistics.

All-cause mortality will be estimated using the Kaplan-Meier product limit method with all available data. Participants who did not die will be censored at the last study day.

Days to clinical improvement and days to recovery will be estimated using a competing risk analysis approach, with death as the competing risk. Participants without the endpoint being analyzed will be censored on the day of the last non-missing ordinal scale assessment.

Forest plots by subgroup will be presented for cumulative incidence of recovery on Day 28.

The number and percent of participants with \geq 1-point improvement, \geq 2-point improvement, and recovery will be presented with 95% confidence intervals on Day 5, Day 7, Day 11, Day 14, Day 28 and last available assessment.

Analyses will be performed using the Expanded RDV-Treated Analysis Set.

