3. GENERAL CONSIDERATIONS FOR DATA ANALYSES

Analysis results will be presented using descriptive statistics. For categorical variables, the number and percentage of participants in each category will be presented; for continuous variables, the number of participants (n), mean, standard deviation (SD) or standard error (SE), median, first quartile (Q1), third quartile (Q3), minimum, and maximum will be presented.

By-subject listings will be presented for all participants in the All Enrolled Analysis Set unless otherwise specified, and sorted by subject ID number, visit date, and time (if applicable). Data collected on log forms, such as AEs, will be presented in chronological order within a participant.

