3.4. Examination of Subject Subgroups

3.4.1. Subject Subgroups for Efficacy Analyses

Selected efficacy endpoints will be analyzed for the following participant subgroups:

- Age (years): (a) < 65 and (b) ≥ 65
- Sex at birth: (a) male and (b) female
- Baseline oxygen support status (based on the 7-point ordinal scale): (a) low flow oxygen, and (b) room air (See Appendix 2)
- Race: (a) Asian, (b) Black, (c) White and (d) Other. Other includes all races (including Not Permitted) other than Asian, Black and White
- Region: (a) North America, (b) Europe, and (c) Asia.

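### Part B duration of hospitalization is summarized only in participants already discharged alive by Day 11 or Day 28, so read as the stay of all treated participants it is too short, mainly at Day 11

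*SAP*

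**What the plan says.** SAP 6.2 lists duration of hospitalization among the efficacy endpoints of interest, counted both from admission and from Day 1. It limits the calculation to stays "for participants who were discharged alive prior to Days 11 and 28, respectively". SAP 6.2.1 repeats the limit with a different boundary: "Duration of hospitalization will be calculated only for participants who are discharged alive on or prior to Days 11 and 28". The result is summarized descriptively, and SAP 3 defines the statistics: "for continuous variables, the number of participants (n), mean, standard deviation (SD) or standard error (SE), median".

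For participants readmitted for COVID-19, SAP 6.2 says that "the hospitalization discharge information is entered in the eCRF database using the latest hospitalization admission".

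Two other endpoints are handled differently: "Days to clinical improvement and days to recovery will be estimated using a competing risk analysis approach, with death as the competing risk". These analyses use the whole Expanded RDV-Treated Analysis Set. No such analysis is planned for hospital discharge. Protocol 3.1 and 8.1.4 list duration of hospitalization without naming a subset, and Protocol 8.5.2 asks only that Part B efficacy endpoints be described.

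**The concern.** Whether a participant enters the summary depends on the quantity being summarized. Counted from Day 1, no stay that runs past the cut-off can appear in the table. Participants still hospitalized contribute nothing, although their stays are the longest, and neither do those who died in hospital. If a share P has been discharged by Day 11, the Day 11 median is really the P/2 percentile of time to discharge among all treated participants.

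Part B is a single arm reported on its own. A Day 11 median without a conditional title could easily be quoted as the typical hospital stay on RDV.

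**Working it through.** **Inputs from the documents (SAP 1.3).** Assumed SOC share not hospitalized at Day 11: 40%. Odds ratio: 1.8. Assumed deaths by Day 11: 0.5%. All are Part A planning values; no Part B discharge rate is given.

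**The plan's own figure.** Under proportional odds the assumed SOC distribution shifts to an RDV distribution whose top category has odds (0.40/0.60) × 1.8 = 1.2, so its share is 1.2/2.2 = 54.5%. Averaging the two distributions gives 1 − Σp³ = 0.875. The sample size formula in SAP 1.3 then gives 88.8% power at 400 participants (200 per group), and 357 participants would be needed for 85%. The stated power above 85% is reproduced, and 54.5% is the Day 11 discharge share that it implies for RDV.

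**Assumptions.** Time from Day 1 to discharge alive follows F(t) = 1 − exp(−(t/s)^k), with k = 1 (exponential), 1.5 or 2. Day 11 is 10 days after Day 1, so s is set by F(10) = P. Besides 54.5%, the values P = 65%, 75% and 85% are assumed, to show faster discharge.

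**Formulas.** The all-participant median solves F(t) = 0.5. The discharged-only median solves F(t) = F(L)/2, with L = 10 for Day 11 and L = 27 for Day 28. The gap is the first minus the second.

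**Results at P = 54.5%, in days from Day 1:**

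| k | s | Median, all | Day 11 median | Gap | Day 28 median | Gap |
|---|---|---|---|---|---|---|
| 1 | 12.68 | 8.79 | 4.04 | 4.75 | 7.37 | 1.43 |
| 1.5 | 11.72 | 9.18 | 5.46 | 3.71 | 8.91 | 0.27 |
| 2 | 11.26 | 9.38 | 6.36 | 3.02 | 9.35 | 0.02 |

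In this case the Day 11 table leaves out 45% of participants, and its median is about the 27th percentile of time to discharge in everyone.

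**Other assumed rates (range over k):**

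| P | Left out at Day 11 | Day 11 gap | Day 28 gap |
|---|---|---|---|
| 65% | 35% | 2.0–2.9 | 0–0.5 |
| 75% | 25% | 1.2–1.6 | 0–0.2 |
| 85% | 15% | 0.6–0.7 | 0–0.03 |

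Adding the planned 0.5% deaths as a competing event changes each gap by less than 0.1 day.

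**Boundary wording.** Excluding Day 11 itself means L = 9. At P = 54.5% this moves 4% to 7% of participants and shifts the Day 11 median by 0.3 to 0.5 days.

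**Choice of target.** The table is for medians. For means, with the curve set so that F(11) = 54.5%, the Day 11 gap is 13.95 − 4.78 = 9.17 days (exponential) and 10.98 − 6.75 = 4.23 days (k = 2). Duration from hospital admission was not quantified, because the documents give nothing on stay before Day 1.

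**The case against.** The SAP states the restriction openly, Part B is descriptive without formal testing (SAP 3.3 and 3.5), and much of the missing information is planned elsewhere. SAP 6.2 sets discharge alive to category 7 and carries it forward unless the participant later dies. SAP 6.2.1 tabulates every category daily to Day 14 and at Day 28 in the full treated set. The category 7 row is thus nearly a cumulative proportion discharged alive, and the day it reaches 50% is the all-participant median. In the 54.5% illustration that is about Day 10, well inside the table.

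Time to clinical improvement helps as well. It is a gain of at least 2 points, or discharge: "improvement from baseline clinical status or discharged alive on the 7-point ordinal scale". From baseline 5 or 6 only discharge alive can satisfy it, so there it equals time to discharge alive. Entry requires SpO₂ above 94% on room air at screening (Protocol 4.2), so this may cover most participants.

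Most of this stands, and it limits the point to presentation. Three things remain:
- The category table is planned without confidence intervals and is not labelled as hospital stay.
- From baseline 4, score 6 in hospital already counts as improvement. The SAP expects such participants, since it plans a subgroup for "Baseline oxygen support status (based on the 7-point ordinal scale): (a) low flow oxygen, and (b) room air". Their share is not given.
- The days of stay actually reported are still those of the discharged subset.

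**Conclusion.** The point holds as a matter of description and labelling. The discharged-only summary understates the stay of all treated participants. At the planning rate implied for RDV the shortfall in the median is about 3.0 to 4.8 days at Day 11 and 0.02 to 1.4 days at Day 28. It shrinks as discharge gets faster. These figures rest on an assumed discharge rate and three assumed curve shapes; they are illustrations, not bounds.

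Three stronger readings are tempting, and the documents do not support them:
- *That the Day 11 median is off by as much as 9 days.* A gap of 9.2 days in the median arises only with the 40% SOC rate and an exponential curve, and every participant in the Part B analysis set receives RDV.
- *That no control arm with the same selection exists.* Part A had an SOC arm and the same protocol endpoint. How it was summarized is set out in a Part A SAP that is not among these documents.
- *That an error rate, power or a treatment comparison is affected.* Part B has none of these.

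**What to change.** Add time from Day 1 to discharge alive in the Expanded RDV-Treated Analysis Set, as a cumulative incidence with death as the competing risk, using the code in SAP Appendix 2 item 11. Report the median where it is reached, and the Day 11, 14 and 28 estimates with 95% confidence intervals. Add a line to Appendix 2 item 16 that censors participants still hospitalized at last contact.

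Use the discharge date that the eCRF holds and say what it means for readmitted participants. SAP 6.2 records discharge from the latest admission, so a first-discharge date may not exist for them.

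Keep the discharged-only durations, but title them *among participants discharged alive* and show beside them the numbers excluded, split into died and still hospitalized. Use one boundary wording in SAP 6.2 and 6.2.1.

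The cost is slightly more programming with existing code, one censoring rule and some table text. The reported stay will look longer than in the Day 11 summary.
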